## **1.4. Clinical Experience**

### **1.4.1. N6LS**

As of August 4, 2021, 27 subjects have enrolled into Groups 1-8. A total of 22 out of 23 subjects enrolled in Groups 1-6 received N6LS study product administrations and completed the protocol. One subject in Group 2 terminated the study after enrolling but prior to product administration. The N6LS product has been administered to 14 subjects by IV infusion and 12 subjects by SC injection. Unsolicited AEs were reported by 16/26 (62%) subjects that received N6LS, with the most frequent events of upper respiratory tract infection (URTI) reported by 6 subjects (23%) and diarrhea reported by 4 subjects (15%). All unsolicited events were mild or moderate in

severity except for one grade 3 diarrhea that began 4 days after administration, spontaneously resolved 2 days later, and was determined to be possibly related to N6LS.

Solicited systemic symptoms were reported in 4/14 (29%) subjects following IV administration and 3/12 (25%) subjects following SC administration. Symptoms reported after IV administration included 4 events of mild headache, 1 mild event each of malaise, chills, and nausea. Symptoms reported after SC administration included 1 mild event each of malaise, myalgia, headache, and nausea. No fevers occurred after IV or SC administration.

Solicited local symptoms reported included moderate bruising (1/14 subjects, 7%) following IV administration. Solicited local symptoms after SC administration included mild pain/tenderness (9/12 subjects, 75%), mild to moderate swelling (4/12 subjects, 33%), mild to severe redness 6/12 subjects, 50%), and mild pruritus (3/12 subjects, 25%).

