#### **4.3.5.     Solicited Adverse Events and Clinical Follow-up**

Subjects will be given a 3-day diary (paper or electronic-based), a thermometer, and a measuring tool. The subjects will use the diary daily as a memory aid to record their highest temperature, local and systemic symptoms, and concomitant medications taken for 3 days after any product administration. Subjects will be provided training on diary completion, proper thermometer usage, and the use of the measuring tool to measure injection site bruising, swelling and redness. Completion of diary card training will be noted in the source documents. Note that while the electronic diary is preferred, subjects will have the option to use a paper diary instead. The paper diary if used, will be transcribed into the study database and stored in the subject file for monitoring purposes.

The signs and symptoms solicited by diary will include systemic events of unusually tired/feeling unwell, muscles aches (outside the injection site), headache, chills, nausea and joint pain; and local (at the product administration site) events of pain/tenderness, swelling, redness, bruising, and pruritus. Subjects will record their highest measured temperature daily for assessment of fever and largest measured diameter of redness, swelling, and bruising at the injection site. Subject diaries will be reviewed by a clinician for accuracy and completeness at follow-up visits. No attribution assessment will be performed for solicited events reported in the diary. Clinicians will follow and collect resolution information for any reactogenicity symptoms that are not resolved within 3 days.

Diary card data will be available in real-time for subjects who use the electronic diary. The clinician may contact the subject by phone if any moderate or severe side effect is reported. Events that may require a clinic visit include rash, urticaria, fever of 38.6°C (Grade 2) or higher lasting greater than 24 hours or significant impairment in the activities of daily living (ADL) (such as those consistent with Grade 2 or higher impairment). Additionally, arthralgia or other clinical concerns may prompt a study visit based on the judgment of a study clinician.

Clinical laboratory assays and clinical evaluations will assess safety and tolerability at specified intervals after each administration. Throughout the study, clinicians will also assess subjects for

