#### **4.6. Criteria for Discontinuation of N6LS or N6LS+ rHuPH20 Administration**

Under certain circumstances, a subject may be prohibited from receiving further study product administrations. These include:

- Pregnancy (female subjects only);
- Grade 3 adverse event assessed as related to N6LS or N6LS+rHUPH20 (with the exception that self-limited Grade 3 solicited reactogenicity will not require discontinuation of product administration);
- Grade 4 adverse event assessed as related to N6LS or N6LS+rHUPH20;
- Immediate hypersensitivity reaction associated with N6LS or N6LS+rHUPH20;
- Intercurrent illness that is not expected to resolve prior to the next scheduled study product administration AND for which PI (or designee) believes is in the best interest of the subject to restrict further exposure;
- Repeated failure to comply with protocol requirements;
- Co-enrollment into a study to receive another investigational research product prior to completion of the requisite study follow-up following the last N6LS product administration;
- The IND sponsor or the study PI decide to terminate the study;
- The IRB, Office for Human Research Protections (OHRP) or the FDA halt the study.

Subjects who have received at least one dose of N6LS but have been discontinued from further study product administrations, will continue with follow-up as shown in the Schedule 5 of the SOE with the exception that research sample collections will be discontinued for pregnant women or others in which it is contraindicated.

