#### **4.7. Criteria for Pausing and Resuming the Study**

Administration of either study product (N6LS or N6LS+ rHuPH20) and new enrollments will be paused by the PI if any of the following criteria is met:

- **One** (or more) subject experiences a serious adverse event (**SAE**) that is assessed as related (possible, probably, or definitely) to the study product, or

- **Two** (or more) subjects experience the same **Grade 3 or higher AE** that is assessed as related (possible, probably, or definitely) to study agent (other than self-limited Grade 3 AEs that resolve during the solicited reactogenicity period).

In the event of a pause, the IND Sponsor Medical Officer (MO) and the PSRT will be promptly notified.

Plan for Review of Pauses and Resuming Rules:

Study product administration and enrollments would resume only if review of the AEs that caused the pause results in a recommendation to permit further study product administrations and study enrollments. The reviews to make this decision will occur as follows:

- **Pauses for related SAEs:** The IND Sponsor Medical Officer (MO), with participation by the PI, will conduct the review and make the decision to resume, amend or close the study. The IRB and FDA will be notified accordingly.
- **Pauses for Grade 3 or higher related AEs:** The IND Sponsor MO, in consultation with the PI, will conduct the review and make the decision to resume, amend or close the study for the Grade 3 or higher AEs that meet criteria for pausing the study. As part of the pause review, the reviewers will also advise on whether the study needs to be paused again for any subsequent events of the same type. The FDA and the IRB will be notified of Grade 3 or higher pause reviews and of the IND Sponsor's decisions.

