### **8.2. Risk/Benefit Assessment**

#### **8.2.1. Potential Risks**

##### Risks of N6LS and mAb Administration

Typically, the side effects of MAbs are mild but may include reactions at injection site (pain, redness, bruising, swelling), fever, chills, rigors, nausea, vomiting, pain, headache, dizziness, shortness of breath, bronchospasm, hypotension, hypertension, pruritus, rash, urticaria, angioedema, diarrhea, tachycardia or chest pain. Up to Grade 3 injection site erythema has been observed after N6LS+ rHuPH20 injection, and some injection site reactions have lasted up to six weeks before completely resolving. Clinical use of MAbs that are targeted to cytokines or antigens associated with human cells may be associated with an increased risk of infections [33]; however, this is not expected to be a risk for a MAb targeted to a viral antigen.

Administration of MAbs may cause immune reactions such as acute anaphylaxis, serum sickness and the generation of antibodies. However, these reactions are rare and more often associated with MAb targeted to human proteins or with the use of murine monoclonal antibodies which would have a risk of human anti-mouse antibodies [33]. In this regard, as N6LS is expected to have a low risk of such side effects since it is directed against a viral antigen and is human in origin.

Published experience with other human MAb directed against the cell surface targets on lymphocytes have shown that infusion of a MAb may be associated with cytokine release, causing a reaction known as "cytokine release syndrome" (CRS) [34]. Most infusion-related events occur within the first 24 hours after beginning administration. Severe reactions, such as anaphylaxis, angioedema, bronchospasm, hypotension and hypoxia, are infrequent and more often associated with MAbs targeted to human proteins or when a non-human MAb, such as a murine MAb, is used [33]. Specifically, with regard to the rare CRS reactions, these generally

occur within the first few hours of beginning the infusion and are more common with the first MAb infusion received. This is because the cytokine release is associated with lysis of the cells targeted by the MAb and the burden of target cells is greatest at the time of the first MAb treatment. With licensed therapeutic MAbs, CRS is managed by temporarily stopping the infusion, administration of histamine blockers and restarting the infusion at a slower rate [35].

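### Read literally, the Section 4.7 pause exemption also covers brief unsolicited Grade 3 AEs, which Section 4.6 does not exempt

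*Combined protocol and SAP*

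**What the plan says.** Section 4.7 has two pause triggers. One related SAE in one subject is enough for the first. The second needs two or more subjects with the same Grade 3 or higher AE "that is assessed as related (possible, probably, or definitely) to study agent", and it carries an exemption: "other than self-limited Grade 3 AEs that resolve during the solicited reactogenicity period". If either trigger is met the pause is mandatory. It leads to review by the IND Sponsor Medical Officer with the PI, and to notification of the FDA and the IRB.

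Section 4.6 governs whether an individual subject may receive further doses. It bars them after a related Grade 3 AE, "with the exception that self-limited Grade 3 solicited reactogenicity will not require discontinuation of product administration".

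Section 4.3.5 sets a 3-day diary and lists the solicited signs. Systemic: tiredness or malaise, muscle aches, headache, chills, nausea, joint pain and temperature. Local: pain, swelling, redness, bruising and pruritus. It adds: "No attribution assessment will be performed for solicited events reported in the diary".

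**The concern.** In Section 4.7 the exempted thing is a Grade 3 AE. The word *solicited* describes the period in which the event must resolve, not the event. In Section 4.6 the exempted thing is solicited reactogenicity. The two sections are adjacent, share the self-limited Grade 3 language, and differ in scope.

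The two-subject rule is the only automatic numeric trigger for non-serious events in a first-in-human study. As printed, it would not respond to a repeated, related, unsolicited Grade 3 reaction that came and went within the 3-day period. Staff would still see such events, but whether dosing stopped would be left to judgment, and the FDA and IRB notice tied to a pause would not follow automatically.

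**Working it through.** **Scope.** Section 4.7 does not state the length of the period; Sections 4.3.5 and 6.3.4 make it 3 days after each administration. Applying the printed text, and then a clause limited to solicited reactogenicity:

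| Event, assessed as related | 4.7 as printed | 4.7 with the narrower clause |
|---|---|---|
| SAE, one subject | pause | pause |
| Same non-serious Grade 4 AE, two subjects | pause | pause |
| Same unsolicited Grade 3 AE, two subjects, not self-limited or lasting past day 3 | pause | pause |
| Same unsolicited, non-serious, self-limited Grade 3 AE, two subjects, resolved by day 3 | **no mandatory pause** | **pause** |
| Same solicited, self-limited Grade 3 reaction, two subjects, resolved by day 3 | no pause | no pause |

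Only the fourth row changes.

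**Is that row empty?** Section 5.1 collects all AEs from first administration through 56 days after each administration, so unsolicited events inside the 3 days are recorded. Section 8.2.1 lists possible effects of monoclonal antibodies that include vomiting and "dizziness, shortness of breath, bronchospasm, hypotension, hypertension, pruritus, rash, urticaria, angioedema, diarrhea, tachycardia or chest pain". Vomiting, dizziness, hypotension, rash, urticaria and diarrhea are not on the Section 4.3.5 diary list. The same section calls such effects typically mild. The row is therefore possible but narrow.

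**What had been seen.** Section 1.4.1 (cut of 4 August 2021) reports every unsolicited event as mild or moderate except "one grade 3 diarrhea that began 4 days after administration, spontaneously resolved 2 days later". Onset on day 4 is after the 3-day period, so that event is not exempt. Observed in the class: 0 of 26 recipients.

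**Who was left to dose.**
- Recipients: 14 IV + 12 SC = 26 (Section 1.4.1).
- Groups 1-6: "A total of 22 out of 23 subjects enrolled in Groups 1-6 received N6LS study product administrations and completed the protocol".
- Recipients in Groups 7-8: 26 - 22 = 4.
- Planned in Groups 7-8: 5 + 5 = 10 (Table 1), so 10 - 4 = 6 remained. Check against the total: 32 - 26 = 6.

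**Chance that the gap matters.** The plan gives no figure for the two-subject rule. Its Table 3 uses a simple binomial: for a rate of 0.10 and n = 5, the chance of at least one event is 1 - 0.9^5 = 0.41, as printed. With the same model, n = 6 and p the assumed per-subject rate of one given event in the class, the chance of two or more cases is

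1 - (1-p)^6 - 6p(1-p)^5

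- p = 0.01: 1 - 0.9415 - 0.0571 = 0.0015
- p = 0.03: 1 - 0.8330 - 0.1546 = 0.012
- p = 0.05: 1 - 0.7351 - 0.2321 = 0.033
- p = 0.10: 1 - 0.5314 - 0.3543 = 0.114

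The rates are assumptions. The first three are the lowest values in Table 3. The exact two-sided 95% upper bound for 0/26 is 1 - 0.025^(1/26) = 0.13, pooling doses and routes.

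**The case against.** The strongest reply is that Sections 4.6 and 4.7 do different jobs, one deciding on re-dosing a subject and the other on stopping everyone. A study-level rule that tolerates brief events more readily would be coherent. That is so, but nothing in the text says the difference was chosen.

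A second reply is that the intent is plain: Section 4.3.5 uses *reactogenicity* for diary symptoms, and Section 4.7 echoes it. That is probably right. It supports calling this loose wording, but a mandatory trigger should not depend on inferred intent.

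A third reply is that other safeguards exist: 4-hour observation (Section 4.3.4), at least 3 days' wait after the first administration at each dose level and route (Section 4), the Day 14 review before Group 8 opens (Table 2), and daily Safety Officer and weekly PSRT review (Section 8.9). The PSRT already includes the PI and a Medical Officer. This stands in part: detection and review are not lost. What is lost is the automatic stop and the notice that goes with it.

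The protection gained is also modest. Groups 7 and 8 receive a single dose, so a pause helps only subjects not yet dosed. After two cases among six, at most 6 - 2 = 4 would remain.

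**Conclusion.** The concern holds as a minor gap in wording. Nothing elsewhere in the protocol narrows the Section 4.7 exemption to solicited events.

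A reader might infer more from Section 4.3.5: solicited events get no attribution, so they can never count as related, and the exemption must act mainly on unsolicited AEs. The documents do not settle this. Section 4.6 carves solicited reactogenicity out of related Grade 3 events, which makes sense only if such events could otherwise count as related. The sections are unclear together, and that lack of clarity is part of the point.

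A reader might also take the 0/26 upper bound as a likely rate. At 0.13 the formula gives 18%, but that rate is the extreme of what the data allow. At 0.20 it gives 34%, for a rate above the bound. Neither is a forecast.

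The size, about 0.1% to 11%, rests on the assumed rates and on 6 undosed planned subjects. That count dates from August 2021, while this version cites December 2021 data and a February 2022 brochure, so fewer may have remained. The permitted accrual of 40 could add subjects.

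**What to change.** Change the Section 4.7 exemption to: *other than self-limited Grade 3 solicited reactogenicity that resolves during the 3-day solicited period*. Section 4.6 can keep its exemption as worded.

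State as well, for both sections, how relatedness applies to solicited events. Without this, it stays open whether a Grade 3 solicited reaction lasting past day 3 can count towards a pause. The question is practical: Section 8.2.1 reports injection-site erythema up to Grade 3 after N6LS with rHuPH20, and some injection-site reactions lasting up to six weeks.

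The cost is one clause and one clarifying statement in an amendment, with no new visits or subjects. The downside of the clause is a slightly higher chance of a pause for Medical Officer review, which is the same probability worked out above. If no such event occurs in two subjects, the clause adds no pause.

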## **5. SAFETY AND ADVERSE EVENTS**

### **5.1. Adverse Events**

An adverse event (AE) is any untoward or unfavorable medical occurrence in a human subject, including any abnormal sign (e.g., abnormal physical exam or laboratory finding), symptom, or disease temporally associated with the use of study treatment, whether or not considered related to the study treatment.

Severity of AEs will be assessed using the *DAIDS Table for Grading the Severity of Adult and Pediatric Adverse Events*, Corrected Version 2.1 [July 2017]. Available from: [https://rsc.techres.com/docs/default-source/safety/division-of-aids-\(daids\)-table-for-grading-the-severity-of-adult-and-pediatric-adverse-events-corrected-v-2-1.pdf](https://rsc.techres.com/docs/default-source/safety/division-of-aids-(daids)-table-for-grading-the-severity-of-adult-and-pediatric-adverse-events-corrected-v-2-1.pdf). Additional information can be found in Appendix II. This grading scale has been used in all prior studies with other HIV-1 bNAbs and will allow for a direct comparison of safety across all available HIV-1 bNAbs.

Reporting of all AEs will occur during the period from first study product administration through 56 days after each study product administration. After this through completion of study participation only serious adverse events (SAEs) and new chronic medical conditions that require ongoing medical management will be recorded as AEs in the study database.

When a subject who receives N6LS coadministered with rHuPH20 experiences an AE assessed by the investigator as related to study product, this attribution reflects relatedness to N6LS and not rHuPH20. Any differences in safety and tolerability between the 5 mg/kg SC N6LS dose without rHuPH20 and 20 mg/kg N6LS SC dose with rHuPH20 will be interpreted as a dose-response difference of N6LS delivered subcutaneously. The extant experience with rHuPH20 indicates that rHuPH20 itself does not confer a unique set of AEs and this protocol will not specifically evaluate rHuPH20 itself for safety and tolerability.

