#### 1.4.2. rHuPH20

As of December 2021, 1,592 subjects were exposed to HYLENEX and other rHuPH20 drug products in 30 clinical studies conducted under IND 66,888, or in post-marketing Phase 4 studies. In partnered trials with co-administered therapeutics, more than 9000 subjects were exposed. Individual doses of rHuPH20 ranged from 15 to 96,000 U (See rHuPH20 IB, section 5.1).

Across all Halozyme-sponsored studies, SC injections of rHuPH20 have been well-tolerated in healthy subjects, dehydrated pediatric subjects, hospice and palliative care subjects, subjects with type 1 and 2 diabetes, and subjects with rheumatoid arthritis. SC injections of rHuPH20 alone or in combination with hydration fluids (Lactated Ringer's, normal saline), co-injected small molecules (morphine, ceftriaxone, ondansetron), peptides (insulin, and insulin analogs), and proteins (IgG and adalimumab) have been well-tolerated in all clinical trials [21, 24]. Most AEs were mild, transient injection site reactions, including erythema, pain, bruising, pruritus, burning, tenderness, edema, induration, irritation, paresthesia, numbness, and rash. Moderate injection site reactions, which have occurred less frequently, include burning, erythema, pain, and numbness. Mild-to-moderate headache was also commonly reported.

rHuPH20 is currently co-formulated with four approved anticancer therapies, trastuzumab (HERCEPTIN HYLECTATM/Herceptin® SC) PHESGOTM (pertuzumab/trastuzumab), Darzalex FASPROTM (daratumumab), and rituximab (i.e., RITUXAN HYCELA®/RITUXAN® SC/MabThera® SC) and dosed sequentially with human immunoglobin to treat primary immunodeficiency (HyQvia®/HYQVIA®).

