**Table 1: VRC 609 Study Schema**

Group	Subjects	Study Products		Dosing Schedule		
		N6LS Dose and Route	rHuPH20 Dose	Day 0	Week 12	Week 24
1	3	5 mg/kg IV	-	X		
2	3	5 mg/kg SC	-	X		
3	3	20 mg/kg IV	-	X		
4	3	40 mg/kg IV	-	X		
5	5	5 mg/kg SC	-	X	X	X
6	5	20 mg/kg IV	-	X	X	X
7	5	5 mg/kg SC	2000 U/mL	X		
8	5	20 mg/kg SC	2000 U/mL	X		
Total	32*	*A total of 32 subjects are planned for enrollment. However, up to 40 subjects may be enrolled to replace subjects who fail to complete the assigned dosing regimen and to meet requests for additional pharmacokinetic (PK) and/or new safety evaluations.				

IV = Intravenous; SC = subcutaneous

Note: rHuPH20 and N6LS are mixed and administered by SC infusion. The dose of rHuPH20 is 2000 Units per mL relative to the N6LS dose volume. Refer to the pharmacy manual for study product preparation and administration instructions.

Enrollment began with the 5 mg/kg dose groups (Groups 1, 2, and 5) when the protocol opened to accrual. Enrollments into the subsequent dose groups (Groups 3, 4, and 6) proceeded after dose-escalation reviews as described in [Section 4.3](#). With implementation of the two N6LS+ rHuPH20 groups as a protocol amendment, Group 7 will open first to accrual, followed by Group 8 pending a dose-escalation review. For each dose level and administration route with or without rHuPH20, the study team will wait at least 3 days following the first product administration before the same dose and administration route of N6LS is administered to additional subjects. Safety review decisions and the status of the enrollment process will be transparent to the Protocol Safety Review Team (PSRT) throughout the trial and discussed

during the weekly and/or monthly safety review. The composition of the PSRT is discussed in [Section 8.8](#).

Safety laboratory samples will be collected throughout the study as per the Schedule of Evaluations (SOE) shown in Appendix I. Subjects will keep a daily diary of solicited systemic symptoms for 3 days after each product administration. PK samples will be collected at specified intervals through 24 weeks after the subject's last product administration.

The study will be conducted at the Vaccine Evaluation Clinic located at the NIH Clinical Center (NIH CC).

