#### **7.5.3. N6LS with rHuPH20: Preparation for SC Administration via Infusion Pump**

For each SC administration order, the subject's weight, dose level, and study group code will be included in the pharmacy order. To prepare a SC administration dose, the pharmacist will calculate the total mg of N6LS and units of rHuPH20 needed to achieve a 2000 U/mL concentration of rHuPH20, and retrieve the minimum number of thawed vials of N6LS and rHuPH20 needed to prepare the full dose (inclusive of infusion tubing residual volume). Prior to preparation for administration, vials of N6LS should be gently swirled for 30 seconds. AVOID FOAMING and DO NOT SHAKE THE VIALS. If particles are observed, follow instructions in Section 7.5. The vial(s) of EDP should be placed at room temperature (20°C to 25°C) for a minimum of 10 to 30 minutes (but for not more than 24 hours at 20°C to 25°C), and then gently swirled and inverted 3-5 times to mix thoroughly.

The required volume of N6LS must be withdrawn from the N6LS vial using a 5 micron filter needle (e.g., BD Blunt Fill Needle – Filter , 18G 1 ½ inch; REF# 305211) and gently injected into a new vial/recipient used for mixing. The required volume of EDP must be withdrawn from the EDP vial using a BD Luer-Lok 1 mL syringe and gently injected into the vial/recipient containing N6LS. The combined N6LS and EDP solution should then be mixed thoroughly by gentle swirling and inversion, 5 to 6 times (~10 seconds), while avoiding foaming. The mixed material can then be drawn into a sterile syringe with size dependent on total fill volume (*Note:* The prepared syringe should contain sufficient volume to accommodate the final dose volume, the priming volume, and the residual volume in the syringe after infusion.) The product may be administered in a single site using an infusion pump and syringe (i.e., Terumo Surflo® 23G winged infusion set with B/Braun extension set [product code ET06L or equivalent] and Medfusion syringe pump or equivalent) at a rate of 2-3 mL/min to ensure accurate and consistent administration. The clinician will use proper SC technique to ensure administration into SC fatty layer.

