#### Risks of EDP Coadministration

EDP coadministration may cause mild, transient injection site reactions, including erythema, pain, bruising, pruritus, burning, tenderness, edema, induration, irritation, paresthesia, numbness, and rash. Moderate injection site reactions have occurred less frequently and include burning, erythema, pain, and numbness. Mild-to-moderate headache is also commonly reported. Adverse events in clinical trials have otherwise reflected the adverse reaction profiles of the co-administered drug or have been associated with the rapid introduction of a relatively large volume of fluid in the SC space.

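### Section 5.1 assigns every related AE after the mixed N6LS and rHuPH20 infusion to N6LS alone, which the design cannot support; the effect is minor and mainly one of interpretation

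*Combined protocol and SAP*

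**What the plan says.** Section 5.1 sets a rule for subjects given the combination. Once the investigator judges an AE related to study product, "this attribution reflects relatedness to N6LS and not rHuPH20". The stated basis is that "rHuPH20 itself does not confer a unique set of AEs", and the section adds that the protocol does not set out to evaluate the enzyme separately. The sentence between the two says that differences in safety between 5 mg/kg SC without the enzyme and 20 mg/kg SC with it will be read as an N6LS dose-response.

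The note to Table 1 says of administration in Groups 7 and 8: "rHuPH20 and N6LS are mixed and administered by SC infusion". Section 7.5.3 describes the preparation: "The combined N6LS and EDP solution should then be mixed thoroughly by gentle swirling and inversion". Section 4.3.4 specifies a single infusion site.

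Section 8.2.1 lists risks of the enzyme product: "EDP coadministration may cause mild, transient injection site reactions". It then continues: "Adverse events in clinical trials have otherwise reflected the adverse reaction profiles of the co-administered drug", or were linked to rapid entry of a large fluid volume.

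**The concern.** A relatedness judgement after one mixed infusion is a judgement about the mixture. Section 5.1 turns it into a statement about one component. The reason offered would justify not studying the enzyme on its own. It does not justify excluding the enzyme as a cause of a particular event. An AE profile that is not unique overlaps with that of N6LS, and overlap makes the components harder to tell apart in someone who received both.

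What is at stake is the first-in-human safety profile of N6LS and the third primary objective, which concerns N6LS given with the enzyme. Read literally, an allergic reaction to the enzyme would be reported as an N6LS reaction.

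**Working it through.** **1. Who is concerned.** Table 1 has four groups of 3 and four of 5: 4 × 3 + 4 × 5 = 32, which matches the stated total. Groups 7 and 8 contribute 5 + 5 = 10, and 10/32 = 31%. Section 1.4.1 shows that some were already dosed by 4 August 2021. Enrolment was 27 overall and 23 in Groups 1-6, so 27 − 23 = 4. Dosing was 14 IV + 12 SC = 26 overall and 22 in Groups 1-6, so 26 − 22 = 4. That is 4/26 = 15% of dosed subjects.

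**2. Which outputs use relatedness.** Section 6.3.3 splits only the unsolicited AE summaries by relationship. Diary events carry no causality assessment (section 4.3.5). The overall AE counts with exact intervals are not split by relationship. The rule therefore bears on unsolicited AEs in Group 7, Group 8, the pooled rHuPH20 summary and the overall summary.

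**3. What the protocol says about the enzyme as a cause.**
- Section 8.2.1 gives EDP coadministration its own list of possible reactions.
- Section 4.1.2, exclusion 8, bars known hypersensitivity to hyaluronidase.
- Section 1.6.2 plans anti-drug antibody testing against rHuPH20 as well as N6LS.
- Sections 4.6 and 4.7 name N6LS+rHuPH20 as the product.
- Appendix II has one relationship scale for the product and no category for a component.
- Section 1.4.2 covers "SC injections of rHuPH20 alone or in combination with hydration fluids", among other combinations, and reports that "Most AEs were mild, transient injection site reactions". This summary is not split by co-injected agent, so it gives no rate for the enzyme alone.

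Only section 5.1 excludes the enzyme as the cause of a related event.

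**4. The dose-response sentence.** Take the maximum weight of 115 kg and 100 mg/mL.
- 5 mg/kg: 115 × 5 / 100 = 5.75 mL, as stated in section 4.3.4, with no enzyme.
- 20 mg/kg: 115 × 20 / 100 = 23 mL of N6LS. Enzyme at 2000 U/mL is 23 × 2000 = 46,000 U. At about 110,000 U/mL this is 46,000 / 110,000 = 0.42 mL. The total is 23.42 mL, as stated in section 4.3.4.

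The two regimens therefore differ in N6LS dose (fourfold), enzyme (none versus up to 46,000 U), volume (up to 5.75 versus 23.42 mL) and delivery (needle injections versus one pump infusion). Group 5 is also dosed three times. N6LS dose is one of several differences.

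**5. Could a group contrast separate the components?** Group 7 (n = 5) and Groups 2 and 5 together (n = 8 planned) share the 5 mg/kg SC dose. With 0/8 events in the comparator, two-sided Fisher p is 0.128 for 2/5 in Group 7 and 0.035 for 3/5. At least 3 of 5 would be needed to reach p < 0.05, and delivery and number of doses differ as well. This is weak group-level evidence and cannot attribute single events.

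**6. What changes under each reading.**
- *Main reading:* the investigator judges the product as given, and section 5.1 then says how to interpret the code. Changing the rule alters no count, percentage or interval. Only the meaning of *related* changes.
- *Other reading:* the investigator judges N6LS only. An event judged to be caused by the enzyme could be coded not related. Section 4.7 pauses the study for one related SAE, or for the same related Grade 3 or higher AE in two subjects, so such an event could fail to count.

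**The case against.** The rule is disclosed, and declining to evaluate rHuPH20 separately is a legitimate choice. Section 1.4.2 cites 1,592 subjects exposed in 30 studies or post-marketing studies, and more than 9000 in partnered trials. Section 8.2.1 says that AEs beyond the listed local reactions and headache have reflected the partner drug or the fluid volume. Charging every related event to N6LS is conservative for the antibody: it may overstate N6LS harm but does not hide it. Safeguards exist. Section 4.7 names the combination, section 5.4 leaves SUSAR decisions to the sponsor, and section 8.9 brings a representative of the enzyme's company into safety reviews while Groups 7 and 8 are active. The exposed set of events is narrow, because many of the listed EDP reactions are diary items without attribution and section 1.2 says the local tissue change reverses within 24-48 hours. The sentence can also be read as defining the coded field, without making a causal claim.

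Most of this stands as a limit on consequence. None of it makes a component-level conclusion supportable from one mixed infusion. If the sentence does define the coded field, the pause-rule ambiguity becomes the issue.

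A reader might infer that a third of the safety table is compromised, since section 6.3.3 names 8 groups, 3 pools and an overall summary (12 groupings) and combination recipients appear in 4. The documents do not support that. Section 6.3.3 fixes no layout, and the same 10 planned subjects are being counted in their own group, in the pool and in the overall summary.

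**Conclusion.** The point holds, at the level of something to consider. Section 5.1 draws a conclusion about one component that the design cannot deliver and that other sections contradict. The effect is on the interpretation of related unsolicited AEs in the 10 planned combination recipients and in the summaries that include them. The number of affected events cannot be estimated, because the documents give no rate of unsolicited AEs caused by the enzyme. It is probably small.

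That no tabulated figure changes rests on the main reading, which fits the order of the sentence: relatedness is assessed first and interpreted afterwards. The text does not exclude the other reading. A reader might go further and infer that the pause rule fails for Groups 7 and 8. That is not established. Section 4.7 names the combination, and under Appendix II an event explained equally well by other causes is still *Possibly Related*, which would keep many events in the related category. What remains is an ambiguity about events that an investigator attributes clearly to the enzyme.

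**What to change.** Replace the attribution sentence in section 5.1 with: *In Groups 7-8, related to study product means related to the product as administered (N6LS, rHuPH20 or their combination, including the SC infusion).* State that this definition governs sections 4.6 and 4.7, Appendix II and the relationship summaries in section 6.3.3.

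Reword the next sentence so that differences between 5 mg/kg SC without the enzyme and 20 mg/kg SC with it are described as differences between regimens. Otherwise the paragraph would contradict the new definition. The statement that rHuPH20 is not evaluated separately can stay.

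Check unsolicited AE attributions already recorded in combination recipients (4 dosed by August 2021, and any since), and change a code only where it departs from the definition.

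The cost is two sentences, a cross-reference and a short check covering the 10 planned subjects. The downside is that relatedness in Groups 7 and 8 will no longer be specific to N6LS, and slightly more events may be coded related.
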